12 FOLLOW-UP DATA COLLECTION (AT 6, 12 AND 18 MONTHS)

Two weeks prior to follow-up visits at 6 and 12 months post baseline, questionnaires and accelerometers will be posted to participants by CTU with instructions for their use and a request to complete the questionnaires and wear the accelerometer for 7 days before the visit. At the meeting the researcher will

REC Ref: 15/SW/0126

• Go through the questionnaire booklet to ensure all questions have been answered

- Check information provided by the participant regarding healthcare service utilisation over the preceding period
- Collect the accelerometer.

In addition, participants will be asked to identify any newly diagnosed conditions or new medications started during the intervention delivery periods, as well as any other management services or interventions used (including commercial weight loss programmes) and any smoking cessation attempts (which can cause substantial weight gain).

At the 18-month assessment, the only quantitative measurements will be weight and waist circumference. See Appendix 2 for the full schedule of quantitative measurements.

Participant travel expenses will be paid for attending, if needed, and those without transport or convenient public transport will be reimbursed for use of a taxi to and from the meeting venue.

13 DURATION OF PARTICIPANT INVOLVEMENT

Each recruited participant is expected to be involved in the study for 18-20 months between the baseline visit and the second follow-up visit.

14 STUDY MEASURES AND DATA COLLECTION

14.1 Trial feasibility measures

To assess the feasibility of a trial of the SkiM intervention, the following measures will be used:

- Recruitment rate (the proportions of participants sent an invitation letter who are enrolled)
- Study completion rate (the proportion of those starting the study who provide data at 18 months). Reasons for dropout or loss to follow-up will be recorded where possible.
- Outcomes completion rates (proportions of participants who complete each measure at each time point)
- Intervention attendance (the proportion attending ≥ 66% of maintenance intervention sessions).

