8 PARTICIPANT IDENTIFICATION

8.1 Method 1: Recruitment via the existing routes used by Intervention Providers

Recruitment to existing Tier 2 weight management services in Devon is through referral by a GP or other NHS health professional. In South Devon and Torbay, referrals are channelled to the Community Fitness Team (CFT) who provide a 12 week group-based weight management programme. In areas around Exeter, referrals are directed to Health Promotion Devon (HPD), a lifestyle hub that helps individuals select a programme from a number that have been commissioned, including group and one-to-one programmes. Trained staff from CFT or HPD staff speak with referred individuals by telephone for screening, information provision and direction to a weight management programme. During these calls, those people who have selected one of the programmes offered by our providers will be asked, using a standard script, if they would be interested in taking part in an extended version of the programme as part of a research study concerned with maintenance of weight loss. Those expressing an interest will be asked to consent to their contact details being given to the research team so that further information about the study can be supplied to them.

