8.2 Method 2 (via GP practice lists)

With help from the Peninsula Clinical Research Network's primary care research network, we have identified research-ready General Practices that are within the catchment area of our intervention providers and represent a diverse demography. The practices will identify patients meeting the study inclusion criteria according to their medical records and send a study invitation letter to a total of 80 potentially eligible people in the first instance. Depending on recruitment rates, letters may be send to further tranches of patients. The letter will be signed by a representative of the Practice and the study manager, and will be accompanied by a leaflet describing the study, a reply slip and a reply-paid envelope addressed to the study team.

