9 RECRUITMENT PROCEDURES

9.1 Participant Invitation

Potentially eligible people who have expressed an interest via either of the routes described in Section 8 will be sent a study information pack, which will include a letter from the study team, the Participant Information Sheet, a reply slip and reply-paid envelope. Different information leaflets will be used

according to whether the individual came through the Torbay hub or the Exeter-based routes, to reflect the programme format available in each area.

Within 7-10 days of sending the information pack, the Study Manager will contact the individual by telephone to check if they are still interested in participation, provide more detailed information about what is involved, and discuss any questions they may have about the study. If they want to participate, they will progress immediately to telephone screening (see below). If they do not, they will be asked if they are willing to say why they chose not to, which will aid the feasibility aim of the study. However it will be made clear that that they are not obliged in any way to disclose reasons. If they agree to give reasons, a brief questionnaire will be used at that point, or sent to the individual with a reply paid envelope if they prefer. Individuals approached through Method 1 (see Section 8) and who decline participation will be referred back to the appropriate hub so they may still participate in their standard weight management programme. Individuals approached through method 2 (see Section 8) and who decline participation will be informed of the possibility of referral to standard weight management programmes, in case they should wish to consider them.

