10.6 Expected recruitment rate

The study requires that 40 participants are recruited over a two-month period for each cohort (This figure maybe revised depending on experiences of programme and study attrition with the first cohort.) Preliminary feasibility work has established that recruitment for the study will require both the standard referral route and additional recruitment from local research-ready General Practice lists. Recruitment will be phased, with invitations sent initially to 80 people across several Practices, with subsequent mailings dependent on response and uptake rates. Assuming a 25% uptake rate, the standard referral routes are expected to produce 20 people per cohort and the Practice route will deliver 20 people per cohort. Experience in recruitment of the first cohort will determine the number of practices and patients to be approached in the second cohort.

SkiM study protocol v8 - 29.03.16

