16.2.1 Stopping conditions

We will consider not continuing on to a trial if a) any serious adverse events are reported or are revealed by the qualitative data that are attributable to the intervention or the study procedures and are deemed by the ethics committee and our independent clinical advisors to constitute an unacceptable risk for further research b) the recruitment rate is less than 15% of those approached c) loss to follow-up rates are greater than 15% per year (this would affect generalisability for a large trial) d) intervention attendance is less than 50% of offered contacts being taken up. These criteria will be developed further by the Project Management Group prior to analysis.

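### Section 14.1 counts the recruitment rate on letters sent, which does not fit the telephone referral route and differs from the people approached in sections 16.2 and 16.2.1

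*Protocol*

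**What the plan says.** Section 14.1 defines the recruitment rate as "the proportions of participants sent an invitation letter who are enrolled". In the same vein, section 16.1 begins the CONSORT participant flow with the number of recruitment letters.

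Other sections count differently. Section 16.2 plans on the share of people contacted and on 133 people to be approached per site. In section 16.2.1, one ground for not going on to a trial is that "the recruitment rate is less than 15% of those approached".

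The two recruitment routes start in different ways:

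- **Referral route (section 8.1).** Hub staff telephone referred people and ask, from a script, "if they would be interested in taking part in an extended version of the programme as part of a research study". Then: "Those expressing an interest will be asked to consent to their contact details being given to the research team".
- **GP-list route (section 8.2).** Practices "send a study invitation letter to a total of 80 potentially eligible people in the first instance".

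Section 9.1 then covers both routes: "Potentially eligible people who have expressed an interest via either of the routes described in Section 8 will be sent a study information pack". The pack includes a letter from the study team.

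In section 10.6, "the standard referral routes are expected to produce 20 people per cohort", with another 20 from the practices, at an assumed uptake of 25%.

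**The concern.** A letter-based denominator treats the two routes unequally. In the GP-list route everyone approached gets a letter, so everyone who declines or does not reply is counted. In the referral route a person who says no on the telephone is never sent anything and drops out of the count. The measure therefore combines two rates with different meanings, and the share of recruits from each route affects the result.

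The term *recruitment rate* also appears in section 16.2.1 with a different denominator, and *approached* is not defined. Two analysts could report different figures under the same name.

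Estimating recruitment is a stated purpose of the study (section 4, objective 4; section 16.2). If the letter-based rate were carried into trial planning as though it were a rate per person approached, the number to approach would be set too low.

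**Working it through.** **1. The plan's own precision figures.** Section 16.2 states 133 approached per site, ±8% at a rate of 30%, and ±6.8% to ±8.5% for rates of 20% to 50%. The 95% half-width is 1.96 × √(p(1−p)/n). With n = 133:

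- p = 0.30: 7.8%
- p = 0.20: 6.8%
- p = 0.50: 8.5%

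Also 133 × 0.30 = 39.9, the stated 40 or so per site. The figures reproduce, with people approached as the denominator.

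**2. Who is counted under section 14.1.**

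| Route | First approach | Who gets papers | Refusers at first approach counted? |
|---|---|---|---|
| Referral (8.1, 9.1) | Telephone script | Only those who express interest and agree to share details | No |
| GP list (8.2) | Letter | Everyone selected for mailing | Yes |

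There is a second reading. The specific term for an invitation letter is used only for the GP-list route; referral recruits get an information pack. On that reading the referral route has no denominator.

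**3. Size of the distortion on the first reading.** Let u be enrolled divided by approached, and f the share of those telephoned who are sent a pack. The referral-route rate on papers sent is u/f. The protocol gives neither f nor the number telephoned, so both are assumed here. With 80 approached per route and the same u in both, the pooled rate on papers sent is (80u + 80u)/(80f + 80) = 2u/(1 + f).

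At the planned u = 25%:

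| f | Referral route, papers sent | Pooled, papers sent | Pooled, approached |
|---|---|---|---|
| 0.8 | 20/64 = 31% | 40/144 = 28% | 40/160 = 25% |
| 0.5 | 20/40 = 50% | 40/120 = 33% | 25% |
| 0.3 | 20/24 = 83% | 40/104 = 38% | 25% |

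In planning terms, at f = 0.5, 100 recruits would appear to need 100/0.333 = 300 approaches, where 100/0.25 = 400 are needed.

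**4. Does it reach the 15% line?** At the planned 25% uptake it does not, since both rates are far above 15%. At lower uptake, with the same formula:

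| u (approached) | f | Pooled, papers sent |
|---|---|---|
| 12% | 0.3 | 19.2/104 = 18.5% |
| 12% | 0.5 | 19.2/120 = 16.0% |
| 12% | 0.6 | 19.2/128 = 15.0% |
| 12% | 0.7 | 19.2/136 = 14.1% |
| 10% | 0.2 | 16/96 = 16.7% |
| 10% | 0.4 | 16/112 = 14.3% |

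The equal split between routes is not essential. Suppose 80 GP letters, 20 enrolled by each route, 200 telephoned and f = 0.3. Then 40/280 = 14.3% of those approached becomes 40/(80 + 60) = 28.6% on papers sent. With 20 enrolled by each route and 80 letters, the pooled rate among those approached falls below 15% only if more than 40/0.15 − 80 = 186.7 people are telephoned, a referral uptake below 20/186.7 = 10.7%.

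**The case against.** A reader might infer that the plan as written can clear the 15% criterion wrongly. The documents do not support that. Section 16.2.1 already specifies those approached. A wrong pass needs three things together: the section 14.1 rate put in place of the one the criterion names, uptake below 15%, and a low share of interested people among those telephoned. At 12% uptake with equal numbers approached, the false pass is gone once f exceeds 0.6. The criterion is also only a ground for considering not continuing, and it is provisional: "These criteria will be developed further by the Project Management Group prior to analysis".

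Nor does the point damage the sample size, which is built on people approached and reproduces. The data are not lost either: section 8.3 has the numbers approached and reaching each recruitment stage logged for each route, so the right rate can be calculated.

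Finally, upward bias depends on how section 14.1 is read. If it means only the practice letter, the GP-list rate is correct and the referral route simply lacks a denominator.

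All of this stands, and it limits the harm. It does not repair section 14.1. Neither reading gives a usable rate across both routes, and the promise to develop the criteria further does not extend to the definition of the measure.

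**Conclusion.** The definition in section 14.1 is wrong as written, on a limited scale. It does not suit a route expected to supply half of each cohort, and it conflicts with the denominators in sections 16.2 and 16.2.1. Followed literally, it either inflates the referral-route rate by 1/f or leaves that route without a rate.

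At the planned uptake, with equal numbers approached, the pooled rate would be about 28% to 38% for f from 0.8 to 0.3, against 25% of those approached. These sizes rest on assumed values of f and of the number telephoned. The inconsistency between sections rests on no assumption. The 15% decision is at risk only if the two rates are interchanged and uptake is well below plan.

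**What to change.** - In section 14.1, define the recruitment rate as people enrolled divided by all people first approached: everyone asked with the standard script in a hub call, plus everyone mailed by a practice.
- Report it by route and by site.
- In section 16.1, start the participant flow at people approached instead of letters sent.
- In section 16.2.1, state that the 15% criterion uses this same rate.
- Keep the proportion enrolled among those sent a pack as a secondary, stage-specific rate.

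The change is one of wording. Section 8.3 already provides for the data, though it depends on the hubs logging everyone asked, including those who decline on the telephone. The sample size is unchanged. The price is a lower reported recruitment rate.

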14.2 Demographic and health data

At baseline assessment, we will collect the following data on participant characteristics:

- Age
- Gender
- Education level
- Occupational status
- Multiple Deprivation index (derived from postcode and national census data)³⁷

REC Ref: 15/SW/0126

SkiM study protocol v8 – 29.03.16

- Ethnicity
- Weight loss history (experience of weight-cycling, use of weight loss programmes, weight loss medications, bariatric surgery)
- Smoking status
- Depression (using the 8-item Patient Health Questionnaire ³⁸)
- Co-morbidities including diabetes and other metabolic disorders, cardiovascular or respiratory disorders, arthritis and other joint disorders, any other conditions that might influence diet or physical activity levels.

These variables have been selected because they may moderate the effects of the intervention.

14.3 Intervention outcome measures

Potential outcome measures for a trial will be used in this study to test processes for collection, their acceptability /feasibility, and to assess outcome completion rates. We will also assess assessment burden using a Study Process Questionnaire which will be completed by participants during the 6 month follow-up visit.

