6.2 Objectives

- 1. To assess the feasibility and acceptability of incorporating the SkiM intervention into existing community-based weight loss programmes.
- 2. To refine the SkiM intervention, including its content and delivery modes, and associated training materials, so as to optimise its individual tailoring, potential effectiveness and feasibility for incorporation into existing community-based weight management programmes.
- 3. To assess the feasibility and acceptability to study participants of recruitment, assessment and process evaluation strategies that may be used in a future trial of the SkiM intervention.
- 4. To determine rates of, and influences on, outcome measure completion, as well as intervention and study participant retention and attrition.
- 5. To estimate the resources needed for the planned future trial.
- 6. To select process and outcomes measures for use in a future trial.
- 7. To develop the framework for economic evaluation in a future trial.

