7 STUDY DESIGN

7.1 Summary of the study design

An action research approach ³⁵ will be used, in which the SkiM intervention is tested and developed in an iterative cycle, involving stakeholders (particularly the service users themselves) in all stages of the process. The cycle involves three iterations of the intervention: an initial version has been developed with the involvement of service users, providers and commissioners as well as academics in the field of health behaviour change; this will be subject to mixed methods evaluation including pre-post testing, the results of which will be used to develop a second iteration of the intervention, which will also be evaluated. A third version of the intervention will then be developed for formal testing in a randomised control trial. This iterative approach involving multiple stakeholders and a pre-post test design, will enable investigation of the feasibility of integrating the SkiM intervention into existing programmes, as well as issues of acceptability, demand and implementation ³⁶. It also facilitates the evaluation and further development of recruitment, assessment and retention methods to be used within a subsequent trial. It is expected that in a trial, the control group would receive best-practice

[figure not shown]
REC Ref: 15/SW/0126

SkiM study protocol v8 - 29.03.16

usual care, which would be an existing weight loss programme. Hence all participants would receive an active intervention, and the need for a control arm is less pressing in a feasibility study.

The intervention period is six months, with outcomes assessment at baseline, and at 6, 12 and 18 months post-baseline. Eighty participants will be allocated equally to one of two study arms with different programme formats: both will be group-based, but they will differ in the number of sessions and supplementary support available. The study will be staged into two cohorts of approximately 40 participants. These will be run sequentially and separated by a period of four months, during which process data collected from the first stage will be used to refine the intervention for delivery in the second phase. This design is illustrated in Figure 1.

Figure 1: Study design

STUDY PARTICIPANTS

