16.2 Sample size considerations

The sample size is calculated to provide realistic estimates (and confidence intervals (CIs)) for the recruitment and study completion rates. The resulting sample size will also allow realistic estimates of the intervention concordance rate and provide an ample pool of participants for qualitative sampling. From recent UK-based trials of interventions to support dietary /physical activity change, it is estimated that 25-30% of those contacted will take part and 70-80% of these will complete measures at 24 months^{46, 47}With a 30% recruitment rate, in order to estimate the recruitment rate with 95% CIs of +/-8% at each site, we would need to approach 133 people at each site (and this would recruit around 40 people per site). If recruitment rates vary between 20 and 50%, the CIs on the estimated recruitment rate would still be acceptable (between +/-6.8 and +/-8.5%). The total sample size requirement for two sites is therefore 80.

This sample size will also allow realistic estimates of the intervention concordance and study completion rates (+/-9 or 10%, assuming 70-80% completion) and provide an ample pool of participants for qualitative sampling (to get feedback on the intervention) in both phases of

intervention development (we would have 2 groups of 10 people receiving the intervention in each phase at each site).

Each of our provider partners will supply 2-3 intervention facilitators (5-6 in total) to deliver the study interventions. It is considered that experience of providing 2-4 complete programmes for 10-20 participants each would give the facilitators sufficient exposure to the intervention to be able to comment on its feasibility and acceptability

If intervention concordance /attendance is lower than expected, we will recruit a higher number (up to 50% more) in the second round to ensure that: a) sufficient people get exposure to the intervention to allow us to get collect a meaningful amount of data on process issues such as acceptability and possible improvements to the programme; b) the facilitators get experience of running several groups; and c) the group size does not become too low to function effectively (if this does still occur, we will consider merging groups to keep the group size above 5 if possible).

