Appendix 3 – Schedule of Intervention Delivery and Process Evaluation

Instrument	Each session	Baseline	Post- programme	Assessment visit 3 (12 months)	Assessment visit 4 (18 months)
Audio-visual recording of session	Х				
Satisfaction questionnaire (client)	Х		Х		
Facilitator records (facilitator) Including self-assessment of each session, contact and non-contact time)	X				
Client logs (e.g. goals, boundaries, weight, physical activity)	Х				
Qualitative interview (client)		Х	X		Х
Qualitative interview (facilitator)			Х		
Study Process Questionnaire			Х		

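### The only direct measure of assessment burden is taken once, at the 6-month visit, with no route for participants who miss that visit

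*Protocol*

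**What the plan says.** Section 14.3 names one instrument for the burden of being assessed: "We will also assess assessment burden using a Study Process Questionnaire which will be completed by participants during the 6 month follow-up visit". Appendix 3 lists the "Study Process Questionnaire" with a single mark, in the post-programme column. The same table has 12- and 18-month columns, and uses the latter for client interviews, but the form is marked in neither.

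Two objectives in section 6.2 need this information. Objective 3 is "To assess the feasibility and acceptability to study participants of recruitment, assessment and process evaluation strategies" that a future trial may use. Objective 4 is "To determine rates of, and influences on, outcome measure completion, as well as intervention and study participant retention and attrition". Section 7.1 sets "outcomes assessment at baseline, and at 6, 12 and 18 months post-baseline".

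Other parts of the protocol bear on the same question:
- Section 14.1 records reasons for dropout or loss where possible, and tabulates completion of each measure at each time point.
- Section 20 invites withdrawers to give reasons, without obliging them. It offers weight-only follow-up in order to limit dropout caused by perceived measurement or attendance burden.
- Section 15.2 provides interviews at 6 and 18 months with a purposive subsample.

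**The concern.** A burden questionnaire that can be completed only at an assessment visit is missing for anyone who skips that visit. If burden is one reason for skipping it, the answers collected are selected towards people who found the assessments tolerable. Section 20 treats perceived measurement burden as a cause of dropout, so the plan itself recognises the mechanism.

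Two smaller issues add to this. The form is completed during a visit at which, under section 12, a researcher goes through the participant's booklet, which may discourage frank criticism. It is also not repeated, so the burden that builds up over later assessments is not rated.

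What is at stake is the choice of measures for the future trial. A burden result that is too favourable could support carrying forward a battery that some participants would not complete.

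**Working it through.** **The protocol's own figures.** The questionnaire has no stated sample size or precision, so the figures to reproduce are those in section 16.2. The 95% half-width is 1.96 × √(p(1−p)/n).
- Recruitment, n = 133 per site: 6.8% at p = 0.2, 7.8% at p = 0.3 and 8.5% at p = 0.5. The protocol gives ±8% at 30% and ±6.8% to ±8.5% over the range 20-50%.
- Completion, n = 80: 10.0% at p = 0.7 and 8.8% at p = 0.8. The protocol gives ±9 or 10%.
- Recruits: 133 × 0.30 = 39.9 per site, about 80 for two sites. This agrees with "The total sample size requirement for two sites is therefore 80".

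These figures reproduce, and the point does not affect them.

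**How many would never be asked.** The inputs are N = 80 and r = 70-80% completion at 24 months, both from section 16.2. The protocol does not say when loss occurs. Assume a constant rate, so that retention at month m is r^(m/24).

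| | r = 0.70 | r = 0.80 |
|---|---|---|
| Retained at 6 months, r^(6/24) | 0.915 | 0.946 |
| Lost by 6 months, of 80 | 6.8 | 4.3 |
| Retained at 18 months, r^(18/24) | 0.765 | 0.846 |
| Lost by 18 months, of 80 | 18.8 | 12.3 |
| Lost between 6 and 18 months | 12.0 | 8.0 |

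About 4-7 people would be gone before the form is offered. Another 8-12 would complete it and be lost later. Two checks on the inputs:
- Loss at 15% per year (the threshold in section 16.2.1) gives 80 × (1 − 0.85^0.5) = 6.2 by 6 months, inside the range.
- The 110 participants in the study summary give 6.0 to 9.4 by 6 months.

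**If loss is early.** Suppose 60-70% of the 18-month loss happens by month 6. Then 0.60 × 12.3 = 7.4 to 0.70 × 18.8 = 13.2, so about 7-13 of 80 would never be asked.

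**How far a result could move.** Let f be the fraction never asked, and p_A and p_N the proportions of attenders and non-attenders who find the assessments burdensome. The true proportion is (1−f)p_A + f·p_N, so reporting p_A understates it by f(p_N − p_A), which cannot exceed f. Under constant loss f is 5.4-8.5%. Under the early-loss assumption it is 7.4/80 = 9.3% to 13.2/80 = 16.5%. These are ceilings, reached only if every non-attender and no attender finds the assessments burdensome.

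**What the other sources supply.** Completion by time point includes non-attenders in its denominator, but it shows what was missed and not why. Reasons for loss are recorded where possible, and withdrawers may decline to give any. The process-evaluation aims in section 15.1 concern the intervention. Follow-up interviewees are sampled on age, gender and success in maintaining weight loss, not on missed assessments.

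**The case against.** The strongest reply is that the protocol does not rely on this form alone. Reasons for loss, questions to withdrawers, weight-only follow-up and measure-by-visit completion all reach beyond 6-month attenders. No estimate, interval or progression criterion in section 16.2.1 uses the questionnaire. This stands, and it is why the point is minor. It does not close the gap, because none of those sources asks non-attenders directly and routinely how burdensome the assessments were.

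A reader might be tempted by four stronger readings that the document does not support.
- *That most loss is expected at 12 and 18 months.* The protocol gives only 24-month completion and an annual threshold. Under constant loss 64-65% of the 18-month loss falls after month 6, simply because 12 of the 18 months lie there. With 60-70% lost by month 6 this reverses.
- *That the form says nothing about later visits.* In Appendix 2 the 12-month battery matches the 6-month one. Section 12 limits quantitative measurement at 18 months to weight and waist. Appendix 2 adds health status and service use there, but no accelerometry, EQ-5D-5L or process scales. A 6-month rating therefore carries over in part; what it cannot show is cumulative burden.
- *That objectives 3 and 4 are answered only from 6-month attenders.* The sources listed above contradict this.
- *That 12-19 people are missing from the burden result.* That count includes the 8-12 who do answer before they are lost. Their ratings can be compared with their later completion, which serves objective 4. Nor does the protocol give any figure for how much loss is caused by burden.

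**Conclusion.** The point holds in a limited form. The only direct burden measure is taken once, from people who attend at 6 months, and non-attenders have no way to complete it. The result is likely to understate burden, although neither the direction nor the amount can be confirmed from the protocol.

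The number never asked is about 4-7 of 80 under constant loss to 70-80% completion at 24 months, and about 7-13 if 60-70% of the 18-month loss falls in the first six months. Both loss patterns are assumptions. Both also equate being lost by 6 months with missing the visit; people who miss only that visit would add to the count. Early loss worsens the selection, and late loss leaves more people rated before their burden has built up.

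Severity is minor. Acceptability of assessment is an objective of this feasibility study, so the measure is worth improving, but no sample size, precision figure or progression rule depends on it.

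**What to change.** Amend section 14.3 and Appendix 3 so that the Study Process Questionnaire is posted to every enrolled participant who reaches the 6-month time point. Include those who miss the visit or stop the programme, and exclude those who ask for no further contact. Have it returned reply-paid direct to the CTU, which also removes completion in front of the researcher. Report the responses and the response rate separately for attenders and non-attenders.

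The cost is postage. The CTU already posts questionnaires before the 6-month visit (section 12), and reply-paid return to the CTU is already used for accelerometers (section 10). The drawbacks are a probably low response from non-attenders and some forms from attenders that would otherwise have been collected at the visit. The non-attender response rate is itself useful feasibility information. A short repeat at 12 months would capture cumulative burden but is optional, since it adds to the burden being measured.
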